A small observational retrospective study on immunocompromised patients (n=33) treated with at least one full course of plitidepsin under compassionate use for the management of COVID-19 is also being carried out as an investigator-sponsored study (see also [Section 1.2.1.3](#)

[Summary from the Clinical Development of Plitidepsin](#) (71). Most of the patients (n=29) received the dose of 2.5 mg/day for three consecutive days, except 4 who had significant comorbidities or organ dysfunction (71). Most received only one course of therapy (n=27), except 6 patients who received a second cycle (71). Patients were elderly, with a mean (SD) age of 67.7 (9.8) years, and 75.8% had received at least one dose of COVID-19 vaccine (71). Immunocompromised status resulted from the therapy of haematologic malignancy (70% of patients), of solid tumor (27.3%), or of an antineutrophil cytoplasm antibody vasculitis (ANCA, 3%) (71). Most patients had comorbidities, including high blood pressure (30.3%), chronic lung disease (15.2%) diabetes mellitus (9.1%), and heart disease (9.1%) (71).

At onset of plitidepsin treatment, 37.9% of patients had severe pneumonia and 62.1% had moderate according to FDA classification; 48.5% were receiving oxygen supplementation; in addition to plitidepsin, 6 patients received IV immunoglobulins and 12 received sotrovimab 500 mg (anti-COVID-19 antibody) (71). The median time from initiation of plitidepsin to SpFi \geq 315 was 8 (95% CI 7; 19) days, the median time for independence from oxygen therapy was 11 (95% CI 10; 26) days, and the median time to first negative qPCR (Ct $>$ 36) was 17 (95% CI 13; 25) days. The mortality rate was 16% (95% CI 3; 37.3) (71).

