6.0 Introduction

This SAP should be read in conjunction with the study protocol and case report form (CRF). Any further changes to the protocol or CRF may necessitate updates to the SAP. A first version of the SAP is expected prior to first patient in (FPI) and final approval of the SAP will occur prior to database lock. Due to low recruitment, early study closure was held on 23Feb24. Therefore, SAP is abridged to provide the essential results for an abbreviated Clinical Study Report (CSR) where information related to safety and descriptive efficacy results will be described. Study objectives, endpoints and populations will be adapted accordingly in order to present the most relevant data.

Consequently, no formal statistical significance tests will be presented, although the descriptive tables will allow a numerical comparison of the characteristics and outcomes of the patients in the experimental and control arm across the subgroups.

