8.2 Overall Design

This is a multi-centre, randomised, controlled, open-label, pragmatic, phase 2 basket study to assess the efficacy and safety of plitidepsin in different groups of immunocompromised patients with coronavirus disease 2019 (COVID-19) who require hospital care.

More than 50 sites are planned to participate in this study worldwide.

[figure not shown]
Approximately 150 patients are foreseen for the study, divided in 4 different groups of immunocompromised patients:

- Group 1 –Patients receiving immune-suppression due to haematopoietic or organ transplantation.

- Group 2 – Patients receiving B-cell depleting therapies.
- Group 3 – Patients receiving other immune-suppressive therapies.
- Group 4 – Other situations with immune deficiencies.

Whenever a patient can be allocated to more than 1 group, the priority will be group 1 > group 2 > group 3 > group 4. In groups 1, 2, and 3, patients will be randomised to receive best standard care (BSC) ± other antiviral (if clinically indicated) on control arm and BSC + plitidepsin on experimental arm. Group 4 will not be controlled (it was not applicable in Spain), as shown in Figure 8.2.1.

Figure 8.2.1. Algorithm for Patient Assignment in NEREIDA Basket Trial.

Stratification:

- Group 1: ISARIC mortality (<9/≥9) | Type of graft (allogeneic haematopoietic/lung or intestinal/other)
- Group 2: ISARIC mortality (<9/≥9) | Disease (haematological neoplasm/other)
- Group 3: ISARIC mortality (<9/≥9) | Disease (neoplasia/other)
- Group 4: Not applicable

Study periods:

The study will include a Screening period, a Treatment period and a Follow-up period.

Refer to the Schedule of Assessments (Protocol Appendix 13) for data to be collected.

The Screening period starts once the patient has provided written informed consent and ends when the patient is randomized (allocated in group 4) in the study. Parameters assessed during this time will serve as the baseline values. The screening procedures should be preferably performed within 24 h prior to administration of study treatment, allowing a maximum of 48 h prior to administration of study treatment if required.

The Treatment period starts on Day 1 (date of randomisation) to 24 h after the last dose of the antiviral therapy; if no antiviral was given in the control arm, then the treatment period will finish on Day 4, for data management purposes. Antiviral treatment must always be started on the randomisation date.

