8.6.2.1 Full Analysis Set (FAS) Population

All randomised patients who have taken at least 1 dose of study treatment (plitidepsin or control) and have completed follow-up for survival until day 30 (± 2). Patients who die before the end of follow-up period will also be included in the FAS population. FAS population will be analysed according to their randomised treatment arm.

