9.0 Conventions and Derivations

Variables reported with different units will be homogenized to standardized variables following the International System of Units (e.g. laboratory tests, biometrical assessments...) unless otherwise specified.

By default, all results will be rounded to one decimal place, except when variables are integer, which will be reported without decimals (e.g., age in years). Percentages for 0 counts will not be presented and 100% values will be presented with no decimal places. For representing p-values four decimals will be selected as default but they could be rounded to fewer decimals if necessary.

Missing values will not be included in the calculation of outputs. Unless otherwise noted, missing data will not be imputed or carried forward.

For patients who discontinue treatment due to adverse events (related or not to study treatment) every effort should be made to remain under study follow-up, anyway, if information is lost before day 28 the conservative value of death will be also imputed.

Patients with no available data for any time-to event efficacy endpoint will be censored at time 0. EOS: Day 60 (± 3) or date of early study termination, if applicable. Patients not yet achieving the time to event endpoint will be censored at the last valid assessment prior to EOS. Efron's method will be used to handle ties.

Assessment windows as specified in the clinical protocol will be respected, see protocol Appendix 13 'Schedule of Assessments and Procedures' for definitions of trial days. Baseline is defined as latest test performed between screening and drug administration.

Change from baseline (%) is defined as: $(\text{test value} - \text{baseline value}) / \text{baseline value} \times 100$.

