11.0 Statistical Methods

Non-continuous variables will be described in frequency tables using counts and percentages. Continuous variables will be described by median, mean, standard deviation (STD), interquartile range (Q1-Q3),

minimum and maximum. Study endpoints will be summarized by means of tables, listings for all CRF variables and figures for temporal series as viral load, lymphocytes/neutrophils evolution, LDH, CT>30 or oxygen necessities as well as Kaplan-Meier figures, as inverse KM (see section 11.8) where time to event data Y-axis started from 0% instead the usual 100%, e.g. time to confirmed negativisation in SARS-CoV-2 antigen test or RT-PCR Ct > 30, will be shown.

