As each basket completes, they would have been evaluated for efficacy, with information gained being used to update the analyses of successive baskets.

Due to the premature study closure no Bayesian specific outputs or sensitivity analyses will be generated

Secondary Endpoints/Other Endpoints

Frequency tables will be prepared for categorical variables, and continuous variables will be described by means of summary tables, which will include the median, mean, standard deviation, interquartile range, minimum, and maximum of each variable.

Frequentist methods will be calculated. Counts and percentages, with their corresponding exact confidence intervals, will be calculated for the binomial endpoints.

Time-to-event variables (e.g. key secondary endpoint) and their set time estimates will be defined as time from randomization to their corresponding event + 1 (see 8.3 section) and analysed according to the Kaplan-Meier method.

Key secondary endpoint, time to confirmed negativisation in SARS-CoV-2 antigen test or RT-PCR Ct > 30, will be analysed according to the Kaplan-Meier method.

<NOTE: Due to the premature study closure no complex specific outputs or sensitivity analyses will be generated>.

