11.6.2 Key Secondary Estimand

The key secondary estimand corresponding to the key secondary endpoint is defined as:

Treatment: Participants will be randomised to receive plitidepsin versus control in each group.

Population: Participants as defined through the inclusion and exclusion criteria, who have been randomised to the trial and who have taken at least 1 dose of study treatment (plitidepsin or control).

Variable:

–Time to confirmed negativisation in SARS-CoV-2 antigen test or RT-PCR Ct > 30 calculated as date/time of survival event – first dose date/time of Investigational Product administration.

Intercurrent events:

- The participant's data are collected and included in the analysis without regard for treatment discontinuation (treatment-policy strategy).
- In the event of the participant initiating another non-protocol therapy, time to confirmed negativisation will be evaluated regardless of initiation of new non-protocol therapy (treatment-policy strategy).

Population level summary: the hazard ratio from a Cox regression for each group comparison including point estimate and confidence interval will be shown.

<NOTE: Due to the premature study closure no complex specific outputs will be generated and descriptive data will be shown>.

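### Patients who die are censored in the recovery curves, so inverse Kaplan-Meier overstates recovery, usually more in the arm with more early deaths

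*SAP*

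**What the plan says.** SAP 9.0 sets the censoring rule for all time-to-event endpoints: "Patients not yet achieving the time to event endpoint will be censored at the last valid assessment prior to EOS". End of study is Day 60 (±3) or early termination. The rule does not mention death.

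SAP 8.6.2.1 keeps deaths in the efficacy set: "Patients who die before the end of follow-up period will also be included in the FAS population". Table 3 in SAP 11.8 assigns unstratified Kaplan-Meier in the FAS to these recovery endpoints:

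- confirmed negativisation (the key secondary endpoint)
- sustained end of hospital care
- sustained symptom improvement and resolution
- sustained oxygen discontinuation
- undetectable viral load or a reduction of more than 2 logs

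SAP 11.0 describes inverse Kaplan-Meier figures, "where time to event data Y-axis started from 0% instead the usual 100"%, with negativisation as its example.

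The key secondary estimand (SAP 11.6.2) lists treatment discontinuation and new non-protocol therapy as intercurrent events, but not death. SAP 6.0 drops formal tests but says that "the descriptive tables will allow a numerical comparison of the characteristics and outcomes of the patients in the experimental and control arm".

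The key secondary endpoint also has two time origins. In SAP 11.6, time-to-event variables "will be defined as time from randomization to their corresponding event + 1"; in SAP 11.6.2 the clock starts at "first dose date/time of Investigational Product administration".

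**The concern.** Censoring suits a patient who could still have the event after leaving observation. A patient who dies before clearing virus, leaving hospital care or coming off oxygen cannot. Kaplan-Meier redistributes that patient's weight to those still at risk, so one minus Kaplan-Meier describes recovery in a hypothetical population without death. It does not estimate the proportion of patients who recovered.

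The censoring is also likely to be informative. FAS entry requires either survival follow-up to Day 30 or death, so censoring before Day 30 will come largely from deaths, plus survivors with missed tests.

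With no formal tests, readers will compare arms by eye on curves, medians and landmark percentages. If one arm has more early deaths, its recovery curve will usually be inflated more. That can shrink or hide a benefit in the other arm.

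**Working it through.** The documents give no figure on this point, so there is none to reproduce. The steps below show the size under stated assumptions.

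**1. Example without a hazard model.** Take 20 patients, the planned arm size in SAP 8.5.

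- Four die on Day 5 and the other 16 all recover. The risk set falls to 16 and the product-limit estimate reaches zero, so inverse Kaplan-Meier shows 100%. True recovery is 16/20 = 80%.
- With one death and 19 recoveries, the curve again shows 100%; the truth is 19/20 = 95%.
- Twelve recover, four on each of Days 8, 15 and 30, after four deaths on Day 5. The curve shows 1 − (12/16)(8/12)(4/8) = 75%; the truth is 12/20 = 60%. If the four deaths fall on Day 40, after the last recovery, the curve shows the correct 60%.

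The bias therefore comes from deaths that precede later recoveries.

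**2. Hazard model: inputs.**

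- Mortality *m* by Day 30: 20% and 7.5% (SAP 8.5 example scenario).
- Median time to recovery: 17 days in both arms. This is an assumption taken from the compassionate-use series in Protocol 1.2.1.3.3, where "the median time to first negative qPCR (Ct $>$ 36) was 17 (95% CI 13; 25) days". That series is single-arm and uses a stricter Ct cut-off than the endpoint's 30.
- Constant hazards, and no deaths after Day 30 (assumptions).

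**3. Formulas.** Recovery hazard hc = ln 2/17 = 0.04077 per day. Death hazard hd = −ln(1 − m)/30 up to Day 30, which is 0.00744 for 20% and 0.00260 for 7.5%.

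- Curve: 1 − KM(t) = 1 − exp(−hc·t)
- True recovery at Day 30: CIF(30) = hc/(hc + hd) × [1 − exp(−30(hc + hd))]
- True recovery at Day 60: CIF(60) = CIF(30) + exp(−30(hc + hd)) × [1 − exp(−30·hc)]

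For m = 20%, exp(−30(hc + hd)) = 0.2354. So CIF(30) = 0.8457 × 0.7646 = 0.647 and CIF(60) = 0.647 + 0.2354 × 0.7057 = 0.813.

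| | Curve, both arms | True, m = 20% | True, m = 7.5% | Overstatement (points) |
|---|---|---|---|---|
| Day 30 | 70.6% | 64.7% | 68.4% | 5.9 vs 2.2 |
| Day 60 | 91.3% | 81.3% | 87.6% | 10.1 vs 3.7 |

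The curves coincide although true recovery differs by about 4 points at Day 30 and about 6 at Day 60.

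**4. Range.**

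- Medians of 8 to 25 days: 5.1–6.3 vs 1.9–2.3 points at Day 30, and 7.3–10.1 vs 2.7–3.7 at Day 60.
- Mortality of 4.4% to 9.6% (recent transplant data in Protocol 1.1), 17-day median: 1.3–2.8 points at Day 30 and 2.2–4.8 at Day 60.
- Different calibration: let 20% and 7.5% be deaths *before recovery* by Day 30, with the death hazard continuing to Day 60. The overstatement is then 10.2 vs 3.7 points at Day 30 and 19.1 vs 7.3 at Day 60. The table counts all deaths by Day 30 and is the more cautious version.

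**5. Direction.** This check used 10,000 random pairs of arms, with medians of 8 to 25 days in the reference arm and 5% to 40% dying before recovery by Day 30. With equal recovery hazards, the arm with more deaths was always the more overstated at Day 30. The order reversed in 4.5% of pairs when the recovery hazard ratio ranged over 0.8–1.25, and in 12.8% when it ranged over 0.5–2.

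**The case against.** **The rule never names deaths.** True: they fall under it by default. But nothing else in either document covers them. SAP 9.0 does impute death when information is lost before Day 28 after discontinuation for an adverse event; that does not say how a death enters a recovery curve. SAP 11.8 defers estimand details to table footnotes and points to a treatment-policy strategy, which cannot settle a recovery outcome after death. The table shells are not available, so handling could be stated there, but the SAP as written leads to censoring.

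**The consequence is limited.** This stands in part. The report is abbreviated, recruitment in groups 1 and 3 was low, no decision rule uses these endpoints, and mortality is tabulated separately. Sampling error is also larger than the bias: at 20 per arm and about 70% recovery, the standard error of a difference is √(2 × 0.7 × 0.3/20) ≈ 14 points, against a between-arm distortion of 5.9 − 2.2 = 3.7 points at Day 30. Imprecision does not excuse a systematic error that is cheap to remove, and a separate mortality table does not let a reader correct the curve.

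**The numbers rest on a planning scenario the trial did not complete.** Correct; they are illustrations and depend on calibration. The model also censors at death, whereas the SAP censors at the last valid assessment. Earlier censoring makes the risk sets smaller, so it would not reduce the overstatement.

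**Section 11.6.2 is partly superseded.** Its closing note replaces the Cox hazard ratio with descriptive data, but the Kaplan-Meier curve remains, and so does the omission of death.

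**Conclusion.** The concern holds. Applied as written, SAP 9.0 censors patients who die before recovering, and the inverse Kaplan-Meier curves then overstate recovery. Under the planning mortality, a 17-day median in both arms and constant hazards, the overstatement is 5.9 vs 2.2 points at Day 30 and 10.1 vs 3.7 at Day 60. At lower mortality it is a few points. The actual size depends on how many deaths occur before the event. The arm with more early deaths is usually the more inflated, but this can reverse if recovery speeds differ greatly or most deaths follow the event.

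The effect is confined to descriptive secondary results. It should be corrected because these curves are what the abridged plan offers for comparing recovery between arms.

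The two time origins are a minor, separate inconsistency. Treatment must start on the day of randomisation (SAP 8.4), so for dosed patients they differ little. SAP 8.2 does allow for controls without an antiviral ("if no antiviral was given in the control arm, then the treatment period will finish on Day 4"), and such patients have no evident first-dose time. Whether they enter the FAS, which requires a dose of study treatment, is itself unclear.

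**What to change.** - In SAP 9.0 and 11.8, state that for the recovery endpoints death before the event is a competing event, and report Aalen-Johansen cumulative incidence by arm in place of inverse Kaplan-Meier. Alternatively, keep patients who die in the risk set as not recovered and censor them at Day 60.
- In SAP 11.6.2, name death as an intercurrent event and say how it is handled.
- Use randomisation as the time origin in both 11.6 and 11.6.2, for both arms.

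The cost is a few sentences and slightly more programming; Protocol 7.1.4 already records the day of death. The reported recovery percentages will be less favourable.

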5.9 EVALUATIONS AT THE END OF STUDY

The following assessments will be performed at Day 60 ± 3 or at the date of early study termination:

	ASSESSMENT/PROCEDURES
Clinical evaluation	
 COVID-19-related signs and symptoms checklist (Appendix 10 – COVID-19 signs/symptoms checklist). Clinical status (11-point WHO Clinical Progression Scale). Vital signs will include body temperature (°C), SBP (mmHg), DBP (mmHg), pulse rate (bpm) and respiratory rate (breaths/min). Targeted physical examination. A targeted physical examination will include heart, lungs, abdomen, extremities plus CNS assessment, based on the investigator's decision as per clinical evolution. Body weight will be measured in kilograms (kg). Lung function tests include PaO₂, FiO₂ and SpO₂. PaO₂/FiO₂ ratio will also be measured; either Ellis or Rice formulae can be used to estimate PaO₂/FiO₂ ratio (Appendix 5 – Imputation of PaO₂/FiO₂ ratio). 
 Concomitant therapies. Subsequent medications for SARS-CoV-2 infection. Subsequent medications for the underlying disease.
Laboratory tests*	
Haematology: haematocrit, RBC, differential WBC counts (including neutrophil and lymphocyte counts), platelet count and haemoglobin (See Appendix 8 – Clinical Laboratory Analyses).
 
Biochemistry: Liver function test [ALT, AP, AST¹, albumin, total bilirubin (direct bilirubin if total is

ASSESSMENT/PROCEDURES	
	abnormally elevated)], LDH, glucose [fasting], sodium, potassium, calcium, BUN/urea, GGT, creatinine, calculated creatine clearance [CKD-EPI], CPK, amylase, lipase, pro-calcitonin, ferritin, and CRP (See Appendix 8 – Clinical Laboratory Analyses).
	Coagulation: D-Dimer (See Appendix 8 – Clinical Laboratory Analyses).
	Urine analysis (semi-quantitative elemental tests for specific gravity, blood, pH, proteins, bilirubin, glucose, ketones, nitrites, and qualitative analysis of the sediment).
Inflammatory and immunological biomarkers in blood (central laboratory)	Luminex® Multiplex cytokine assessment.
Anti-SARS-CoV-2 (central laboratory)	IgG/M anti-protein S and N.
	T-cell response (IFN- γ) to SARS-CoV-2 S-protein (Quantiferon®).
Detection of SARS-CoV-2	qRT-PCR in oro/naso-pharyngeal exudates (central laboratory).
	Rapid Antigen Test (at site, provided by the Sponsor).

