7. STUDY EVALUATIONS

7.1 EFFICACY

7.1.1 Test for COVID-19

A SARS-CoV-2 Rapid Antigen Test, provided by the Sponsor, will also be performed at the site by the research team on Day 4 until discharge, and always at Days 1, 4 (± 1 day), 8 (± 1 day), 15 (± 1 day), 30 (± 2 days), 45 (± 2 days), and 60 (± 3 days); if RAT is positive at discharge, RAT should also be monitored on a weekly basis until negative. A negative result should be confirmed with a second RAT within 48 h, by the investigator team.

Quantitative PCR to assess viral load on Day 1 before initiation of treatment and on Days 4 (± 1 day), 8 (± 1 day), 15 (± 1 day), 30 (± 2 days), 45 (± 2 days), and 60 (± 3 days) (see [Appendix 13 - Schedule of Assessments and Procedures](#)), will be performed by a central laboratory. Based on these assessments, changes in viral load respect to Day 1 will be calculated for each patient. The proportion of patients with either $> 2 \log 10$ reductions or undetectable SARS-CoV-2 on each time point will also be assessed.

Details regarding the collection, processing, storage, and shipment of oro-nasopharyngeal samples for qPCR testing will be provided to each investigational site before initiation of the study in the form of a laboratory manual. All oro-nasopharyngeal samples for qPCR must be

processed and shipped as specified in the laboratory manual to maintain sample integrity. Any deviations from the processing steps (e.g., sample collection and processing steps, interim storage, or shipping conditions), including any actions taken, must be documented and reported to the Sponsor. On a case-by-case basis, the Sponsor may make a determination as to whether sample integrity has been compromised. Any deviation from the specified sample handling procedure that results in compromised sample integrity will be considered a protocol deviation.

Samples will be analysed using validated analytical methods, as approved by the Sponsor.

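### SAP 9.0 censors event-free patients before the EOS visit although that visit can produce events, which biases the tail of the virological Kaplan-Meier curves upward

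*SAP*

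**What the plan says.** SAP 9.0 sets the boundary, "EOS: Day 60 (± 3) or date of early study termination, if applicable", and then the censoring rule: "Patients not yet achieving the time to event endpoint will be censored at the last valid assessment prior to EOS". It does not say whether a result obtained at the EOS visit counts as *prior to EOS*.

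Protocol 5.9 makes EOS an assessment visit: "The following assessments will be performed at Day 60 ± 3 or at the date of early study termination". Its list includes "qRT-PCR in oro/naso-pharyngeal exudates (central laboratory") and "Rapid Antigen Test (at site, provided by the Sponsor"). Neither document excludes an event first seen there.

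Between visits, Protocol 7.1.1 adds antigen tests: "if RAT is positive at discharge, RAT should also be monitored on a weekly basis until negative". Protocol 5.8 asks for RAT every other day while the patient is admitted. Scheduled central PCR has nothing between Day 45 and Day 60.

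SAP Table 3 keeps unstratified Kaplan-Meier as the only analysis of the key secondary endpoint (confirmed antigen negativisation or Ct > 30), and keeps it for time to undetectable viral load or a reduction of more than 2 logs. SAP 11.0 plots these as inverse curves, "where time to event data Y-axis started from 0% instead the usual 100"%.

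**The concern.** At a visit that can yield an event, patients with and without the event should both be at risk on that day. Under the literal rule those still positive at EOS have already left the risk set, so whether the EOS result is used depends on what it shows. That is informative censoring. The risk set at EOS shrinks towards the patients who cleared there, and the last step of the curve is too large. The same can happen at an early-termination visit, because the SAP's definition of EOS includes it.

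What is at stake is the description of late non-clearance. Protracted infection is part of the stated rationale (Protocol 1.3), and the abridged SAP has dropped the Bayesian, Cox and sensitivity analyses that would otherwise stand beside this curve.

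**Working it through.** The plan gives no figure that depends on the censoring rule, so there is nothing to reproduce. All clearance rates and event splits below are assumptions. The documents supply only the visit days, the planned 20 patients per arm, and the 17-day median to PCR negativity from compassionate use (Protocol 1.3).

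**1. A single arm.** The inverse Kaplan-Meier estimate is 1 − ∏(1 − d/n), with d events among n at risk. Assume 20 patients: 14 events by Day 45, 2 first negative at Day 60, 4 still positive at Day 60. At Day 45 both rules give 14/20 = 70%.

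- Literal rule, the 4 censored at Day 45: n = 2, d = 2 at Day 60, so 1 − 0.30 × (1 − 2/2) = 100%.
- Censored at Day 60: n = 6, d = 2, so 1 − 0.30 × (1 − 2/6) = 80% = 16/20, the true proportion.

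Other splits of the last 6 patients:

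| First negative at Day 60 | Still positive | Literal | Including EOS |
|---|---|---|---|
| 3 | 3 | 100% | 85% |
| 1 | 5 | 100% | 75% |
| 0 | 6 | 70% | 70% |

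The last row shows that without an EOS event there is no jump.

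**2. Expected size.** Assume exponential clearance with median m, so S(t) = 2^(−t/m), with every EOS visit on Day 60 and no other censoring. Let p be the day of the last test before EOS and q = S(p) − S(60) the chance that a patient is first negative at EOS. Under the literal rule the curve ends at 100% if at least one of the 20 has an EOS event. Otherwise it stays at its Day p value. The expected final value is

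1 − (1 − q)^20 × S(60)/(1 − q).

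For m = 30 and p = 45 (PCR schedule): q = 0.3536 − 0.2500 = 0.1036, and (1 − q)^20 = 0.112. The result is 1 − 0.112 × 0.279 = 97%, against a true 75%. The curve ends at 100% in about 89% of arms.

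For m = 30 and p = 57 (weekly RAT on Days 15, 22, …, 57): q = 0.2679 − 0.2500 = 0.0179, and (1 − q)^20 = 0.696. The result is 1 − 0.696 × 0.255 = 82%, against 75%. The curve ends at 100% in about 30% of arms.

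| Median | True Day 60 clearance | Literal, last test Day 45 | Literal, weekly RAT |
|---|---|---|---|
| 17 days | 91% | 98% | 93% |
| 30 days | 75% | 97% | 82% |

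Simulation of 2,000 arms per scenario agrees with these values within simulation error.

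**3. Spread EOS dates.** With weekly RAT and EOS visits on Days 57–63, simulated final values (n = 20) were 94% literal against 92% when censored at EOS for median 17 days, and 85% against 78% for median 30 days.

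**4. What does not change.** Up to the last test before EOS the two rules give the same curve. Under the same assumptions that is 71% v 50% at Day 30 and 84% v 65% at Day 45 for medians of 17 and 30 days.

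**The case against.** The strongest reply is that *prior to EOS* ordinarily means up to EOS, so this is loose wording and not an error. That may be what the sponsor intends, but the SAP does not say it, and a programmer following the words would drop the EOS result for non-events only.

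Three stronger readings are tempting, and the documents do not support them.

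- A reader might infer that the curve must end at 100%. It does so only if at least one event is first seen at EOS and nobody else is then at risk. Weekly or alternate-day RAT and the ±3-day window can both prevent that. A first negative RAT at EOS also needs a repeat: "A negative result should be confirmed with a second RAT within 48 h, by the investigator team". A new Day 60 event is therefore surest through PCR.
- A reader might infer that a real difference in persistent infection would vanish. On the sparse grid the Day 60 contrast of 91% v 75% does shrink to 98% v 97%, but the curves to Day 45 stay apart, and with weekly RAT the Day 60 contrast remains visible (93% v 82%). Table 3 also keeps the Day 60 percentage with undetectable viral load, and SAP 11.0 provides listings.
- A reader might extend the point to every time-to-event endpoint. Symptom improvement and resolution need 4 consecutive days, oxygen discontinuation 7 days, and sustained discharge 30 days without readmission. A single EOS visit cannot newly establish any of these, so this mechanism does not materially affect them.

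It is also fair that the stakes are limited. SAP 6.0 presents no formal significance tests, and actual arms are smaller than the planned 20 in at least some cohorts.

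**Conclusion.** The point holds as an asymmetry in a stated rule that biases the tail of two virological Kaplan-Meier curves upward. For time to undetectable viral load or > 2 log reduction, the full Day 45 to Day 60 gap applies, because antigen tests cannot inform it: about 97% against a true 75% at an assumed median of 30 days. For the key secondary endpoint, the extra RATs reduce the bias to about 82% against 75%, and to 93% against 91% at a median of 17 days. If the weekly tests are missed, the bias moves back towards the sparse-grid figures.

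These sizes rest on the strict reading of *prior to EOS*, exponential clearance and 20 patients per arm. Medians and estimates reached before the last pre-EOS test are unaffected, and no test or model result depends on the rule. It is worth correcting because the curve is the only remaining analysis of the key secondary endpoint.

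**What to change.** Replace the sentence in SAP 9.0 with: *Patients without the event will be censored at the last valid assessment on or before EOS, including the EOS or early-termination visit itself.* Apply it to the key secondary endpoint and to time to undetectable viral load or > 2 log reduction.

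Show numbers at risk under both curves, at least from Day 45. The corrected rule does not remove small-sample tail effects: in one simulated scenario (10% first negative at EOS, 20% still positive, EOS on Days 57–63), censoring at the actual EOS date still ended at 100% in about 28% of the arms that had both kinds of patient, because the last event can fall after everyone else's EOS date.

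The cost is one sentence, a one-line programming change and a risk table. No extra data are needed, and if the sponsor already meant up to and including EOS, no result changes.
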